- B. H_1^2 : 50 µg mRNA-1273.529, as a single booster dose, against the variant B.1.1.529 is non-inferior to the booster dose of (50 µg) mRNA-1273 against B.1.1.529 based on the difference in SRR at Day 29 with a non-inferiority margin of 10%.
- C. H_1^3 : 50 µg mRNA-1273.529, as a single booster dose, against the variant B.1.1.529 is superior to the booster dose of (50 µg) mRNA-1273 against B.1.1.529 based on the GMT ratio of mRNA-1273.529 against the variant B.1.1.529 at Day 29 compared to mRNA-1273 against the variant B.1.1.529 at Day 29.

An ANCOVA model will be performed to assess the difference in immune response between mRNA-1273.529 and mRNA-1273 (using external comparator) as the first booster dose. For immune response against the B.1.1.529 strain, in the ANCOVA model, antibody titers at Day 29 postbooster against the B.1.1.529 strain will be a dependent variable, and a group variable (mRNA-1273.529 and mRNA-1273) will be the fixed effect, adjusting for age groups (< 65, ≥ 65 years) and prebooster antibody titer level, if applicable.

The GMT will be estimated by the GLSM from the model and its corresponding 95% will be provided for each group. The GMR (ratio of GMTs) for mRNA-1273.529 with respect to mRNA-1273 will be estimated by the ratio of GLSM from the model and the corresponding 95% CIs will be provided. The 95% CI for GMR will be used to assess the between group difference in immune response against the B.1.1.529 strain for mRNA-1273.529 at Day 29 compared to the mRNA-1273.

The number and percentage (rate) of participants achieving seroresponse at Day 29 will be summarized with 95% CI calculated using the Clopper-Pearson method for each group. The difference of SRR between mRNA-1273.529 and mRNA-1273 will be calculated with 95% CI based on Miettinen-Nurminen method. The non-inferiority in SRR of mRNA-1273.529 compared to mRNA-1273 will be considered demonstrated if the lower bound of the 95% of the SRR difference is > -10% based on the non-inferiority margin of 10%.

The primary immunogenicity objective (against the B.1.1.529) is considered met if non-inferiority is demonstrated based on GMR and SRR difference, specifically:

- The lower bound of the 95% CI of the GMT ratio between mRNA1273.529 against the variant (B.1.1.529) at Day 29 as compared to 50 µg mRNA1273 against B.1.1.529 at Day 29 is > 0.667 based on the non-inferiority margin of 1.5

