- The lower bound of the 95% CI of the SRR difference (50 µg mRNA-1273.529 against the variant B.1.1.529 at Day 29— 50 µg mRNA-1273 against B.1.1.529 at Day 29) is >-10%
- If non-inferiority is demonstrated (based on GMT ratio and SRR difference), the lower bound of 95% CI of the GMT ratio will be compared to 1, if it's greater than 1, then superiority is demonstrated.

Cohort 2:

The same analyses methods described in Part F Cohort 1 will be used for Cohort 2.

- A. H_1^1 : 50 µg mRNA-1273.529, as a second booster dose, against the variant B.1.1.529 is non-inferior to the second booster dose of (50 µg) mRNA-1273 against B.1.1.529 based on the GMT ratio of mRNA-1273.529 against the variant B.1.1.529 at Day 29 compared to mRNA-1273 against the variant B.1.1.529 at Day 29 with a non-inferiority margin of 1.5.
- B. H_1^2 : 50 µg mRNA-1273.529, as a second booster dose, against the variant B.1.1.529 is non-inferior to the second booster dose of (50 µg) mRNA-1273 against B.1.1.529 based on the difference in SRR at Day 29 with a non-inferiority margin of 10%.
- C. H_1^3 : 50 µg mRNA-1273.529, as a second booster dose, against the variant B.1.1.529 is superior to the second booster dose of (50 µg) mRNA-1273 against B.1.1.529 based on the GMT ratio of mRNA-1273.529 against the variant B.1.1.529 at Day 29 compared to mRNA-1273 against the variant B.1.1.529 at Day 29.

The primary immunogenicity objective (against the B.1.1.529) is considered met if non-inferiority is demonstrated based on GMR and SRR difference, specifically:

- The lower bound of the 95% CI of the GMT ratio between mRNA1273.529 against the variant (B.1.1.529) at Day 29 as compared to 50 µg mRNA1273 against B.1.1.529 at Day 29 is > 0.667 based on the non-inferiority margin of 1.5.
- The lower bound of the 95% CI of the SRR difference (50 µg mRNA-1273.529 against the variant B.1.1.529 at Day 29— 50 µg mRNA-1273 against B.1.1.529 at Day 29) is >-10%.
- If non-inferiority is demonstrated (based on GMT ratio and SRR difference), the lower bound of 95% CI will be compared to 1, if it's greater than 1, then superiority is also demonstrated.

Part G:

50 µg mRNA-1273.214 as the second booster dose will be compared to 50 µg mRNA-1273 as the second booster dose (active control arm in Part F, Cohort 2)

For the primary immunogenicity objective, there are 4 hypotheses to be tested at Day 29 and 4 hypotheses to be tested at Day 91.

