- B. H_1^{10} : 50 μ g mRNA-1273.214, as a second booster dose, against ancestral SARS-CoV-2 is non-inferior to the booster dose of (50 μ g) mRNA-1273 against ancestral SARS-CoV-2 based on the difference in SRR at Day 91 with a non-inferiority margin of 10%.

If the lower bound of the 97.5% CI of the SRR difference (50 μ g mRNA-1273.214 against ancestral SARS-CoV-2— 50 μ g mRNA-1273 against ancestral SARS-CoV-2) is >-10% at Day 29 or Day 91, then the key secondary objective will be considered met.

In the event that an early assessment of the 1273.214 data is needed due to public health concerns, a two-staged approach might be used. Specifically, a subset of participants' (ie, 50 first enrolled participants) serum samples will first be tested against ancestral SARS-CoV-2 and variants of concern. For the Day 29 and Day 91 immunogenicity analyses, all participants' immune data will be used in the formal interim analysis to evaluate the primary immunogenicity objective.

Part H:

The primary immunogenicity objective will be assessed in the per-protocol immunogenicity, SARS-CoV-2 negative set.

The analyses methods described in Part F Cohort 1 will be used for Part H.

The primary immunogenicity objective is considered met if non-inferiority against Omicron BA.4/5 and ancestral SARS-CoV-2 D614G based on GMR and SRR difference at Day 29 is demonstrated.

Non-inferiority against Omicron BA.4/5:

- The lower bound of the 95% CI of the GMT ratio between mRNA-1273.222 against Omicron BA.4/5 at Day 29 as compared to 50 μ g mRNA-1273 against BA.4/5 at Day 29 is > 0.667 based on the non-inferiority margin of 1.5.
- The lower bound of the 95% CI of the SRR difference (50 μ g mRNA-1273.222 against Omicron BA.4/5 at Day 29— 50 μ g mRNA-1273 against BA.4/5 at Day 29) is >-5%.

Non-inferiority against ancestral SARS-CoV-2 D614G:

- The lower bound of the 95% CI of the GMT ratio between mRNA-1273.222 against ancestral SARS-CoV-2 D614G at Day 29 as compared to 50 μ g mRNA-1273 against ancestral SARS-CoV-2 D614G at Day 29 is > 0.667 based on the non-inferiority margin of 1.5.
- The lower bound of the 95% CI of the SRR difference (50 μ g mRNA-1273.222 against ancestral SARS-CoV-2 D614G at Day 29— 50 μ g mRNA-1273 against ancestral SARS-CoV-2 D614G at Day 29) is >-10%.

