6.4.2 (Selecting P201B Subjects as External Comparator)	Removed P301 (COVE) study as historical control for Study Parts A.1, B, C, and D.	No longer applicable per protocol amendment 11.
6.4.3 (Primary Analysis of Antibody-Mediated Immunogenicity Endpoints), 6.4.4 (Secondary Analysis of Antibody-Mediated Immunogenicity Endpoints), 6.4.5 (Exploratory Analysis of Antibody-Mediated Immunogenicity Endpoints)	Removed analyses that are no longer applicable.	Updated according to protocol amendment 11.
6.5.5 (Sequencing)	New section added.	Added analysis strategy for exploratory objective.

This SAP provides statistical analysis details/data derivations. It also documents modifications or additions to the analysis plan that are not “principal” in nature and result from information that was not available at the time of protocol finalization. If the methods in this SAP differ from the methods described in the protocol, the SAP will prevail.

Study mRNA-1273-P205 is a phase 2/3, open-label study to evaluate the immunogenicity, safety, and reactogenicity of mRNA-1273.211, mRNA-1273, mRNA-1273.617.2, mRNA-1273.213, mRNA-1273.529, mRNA-1273.214, mRNA-1273.222, mRNA-1273.815, and mRNA-1273.231 vaccines. The study consists of 9 parts: Part A.1 will evaluate 2 dose levels (50 or 100 µg) of mRNA-1273.211, Part B will evaluate a single dose of 100 µg mRNA-1273, Part C will evaluate 2 dose levels (50 or 100 µg) of mRNA-1273.617.2, Part D will evaluate 2 dose levels (50 or 100 µg) of mRNA-1273.213, Part E will evaluate a single dose of 100 µg mRNA-1273.213 at a single clinical study site, Part F Cohort 1 will evaluate 50 µg of mRNA-1273.529 as a single booster, Part F Cohort 2 will evaluate 50 µg of the mRNA-1273.529 vaccine or 50 µg of the mRNA-1273 as a second booster in individuals who have previously received a single booster dose of 50 µg mRNA-1273, Part G will evaluate 50 µg of mRNA-1273.214 as a second booster in individuals who have previously received a single booster dose of 50 µg mRNA-1273, Part A.2 will evaluate 50 µg of mRNA-1273.214 as a second booster in individuals who have previously received the mRNA-1273.211 booster, Part H will evaluate 50 µg of mRNA-1273.222 as a second

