6.4.3. Primary Analysis of Antibody-Mediated Immunogenicity Endpoints

Part A.2

For Part A.2 participants, Day 29 and Day 181 immune response after mRNA-1273.214 (50 µg) as a second booster dose will be compared with their own Day 29 and Day 181 immune response of mRNA-1273.211 (50 µg) received as the first booster dose. GMT ratios will be calculated by back transforming the mean of paired differences of antibody titer data on the logarithmic scale between Day 29 and Day 181 post mRNA-1273.214 and Day 29 and Day 181 of antibody titer data post mRNA-1273.211. CIs for the GMT ratio will be based on t-distribution of the log-transformed values then back transformed to the original scale for presentation. Seroresponse rates at Day 29 and Day 181 post mRNA-1273.214 will be compared with their seroresponse rates at Day 29 and Day 181 post

mRNA-1273.211. The difference in seroresponse rates and its corresponding 95% CI based on adjusted Wald method will be provided.

Part F Cohort 1

Primary analysis set for immunogenicity objectives will be based on PPIS-Neg.

For the primary objective on immune response for a first booster dose of 50 μ g mRNA-1273.529, see [Section 4.2](#). An analysis of covariance (ANCOVA) model will be performed to assess the difference in immune response between mRNA-1273.529 and mRNA-1273 (P201B 50 μ g booster after 100 μ g primary series) as the first booster dose. For immune response against the B.1.1.529 strain, in the ANCOVA model, antibody titers at Day 29 post-booster against the B.1.1.529 strain will be a dependent variable, and a group variable (mRNA-1273.529 and mRNA-1273) will be the fixed effect, adjusting for age groups (< 65 , ≥ 65 years) and pre-booster antibody titer level if applicable; the model may also be adjusted for other characteristics.

The GMT will be estimated by the GLSM from the model and its corresponding 95% will be provided for each group. The GMR (ratio of GMTs) for mRNA-1273.529 with respect to mRNA-1273 will be estimated by the ratio of GLSM from the model and the corresponding 95% CIs will be provided. The 95% CI for GMR will be used to assess the between group difference in immune response against the B.1.1.529 strain for mRNA-1273.529 at Day 29 compared to the mRNA-1273.

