The primary immunogenicity objective (against the B.1.1.529) is considered met if non-inferiority is demonstrated based on GMR and SRR difference, specifically:

- The lower bound of the 95% CI of the GMT ratio between mRNA1273.529 against the variant (B.1.1.529) at Day 29 as compared to 50 µg mRNA-1273 against B.1.1.529 at Day 29 is > 0.667 based on the non-inferiority margin of 1.5.
- The lower bound of the 95% CI of the SRR difference (50 µg mRNA-1273.529 against the variant B.1.1.529 at Day 29 - 50 µg mRNA-1273 against B.1.1.529 at Day 29) is >-10%.

- If non-inferiority is demonstrated (based on GMT ratio and SRR difference), the lower bound of 95% CI of GMT ratio will be compared to 1, if it's greater than 1, then superiority is demonstrated.

Analyses for the primary immunogenicity endpoints may also be performed using Per-Protocol Immunogenicity Set similar to Part F Cohort 1.

Part G

Primary analysis set for immunogenicity objectives will be based on PPIS-Neg.

50 µg mRNA-1273.214 as the second booster dose will be compared to 50 µg mRNA-1273 as the second booster dose (active control arm in Part F, Cohort 2). For the primary objective on immune response for a second booster dose of 50 µg mRNA-1273.214, hypotheses are to be tested at Day 29 and Day 91 (see [Section 4.2](#)). For the primary objective of immune response, an alpha of 0.05 (two-sided) will be allocated to the two time points. Day 29 and Day 91 will each have an alpha of 0.025 (two-sided) for hypotheses testing. The analyses method described in Part F Cohort 1 will be used for Part G.

The primary immunogenicity objective is considered met if non-inferiority against B.1.1.529 based on GMR and SRR difference and non-inferiority against the ancestral SARS-CoV-2 based on GMR are demonstrated based on GMR at Day 29 or Day 91.

Day 29: alpha = 0.025 (2-sided)

- The lower bound of the 97.5% CI of the GMT ratio between mRNA-1273.214 against the variant (B.1.1.529) at Day 29 as compared to 50 µg mRNA-1273 against B.1.1.529 at Day 29 is > 0.667 based on the non-inferiority margin of 1.5.
- The lower bound of the 97.5% CI of the SRR difference (50 µg mRNA-1273.214 against the variant B.1.1.529 at Day 29 - 50 µg mRNA-1273 against B.1.1.529 at Day 29) is >-10%.
- The lower bound of the 97.5% CI of the GMT ratio between mRNA-1273.214 against ancestral SARS-CoV-2 at Day 29 as compared to 50 µg mRNA-1273 against ancestral SARS-CoV-2 at Day 29 is > 0.667 based on the non-inferiority margin of 1.5.

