An analysis of covariance (ANCOVA) model will be performed to assess the difference in immune response between mRNA-1273.222 and mRNA-1273. In the ANCOVA model, antibody titers at Day 29 post-booster against the Omicron BA. 4/5 strain will be a dependent variable, and a group variable (mRNA-1273.222 and mRNA-1273) will be the fixed effect, adjusting for age, pre-booster antibody titer level if applicable; the model may also be adjusted for other characteristics. Age group (≥ 65 , < 65 years) or age as continuous variable may be considered in the ANCOVA model.

The GMT will be estimated by the GLSM from the model and its corresponding 95% will be provided for each group. The GMR (ratio of GMTs) for mRNA-1273.222 with respect to mRNA-1273 will be estimated by the ratio of GLSM from the model and the corresponding 95% CIs will be provided. The 95% CI for GMR will be used to assess the between group difference in immune response against the BA. 4/5 strain for mRNA-1273.222 at Day 29 compared to the mRNA-1273.

The number and percentage (rate) of participants achieving seroresponse at Day 29 will be summarized with 95% CI calculated using the Clopper-Pearson method for each group. The difference of SRR between mRNA-1273.222 and mRNA-1273 will be calculated with 95% CI based on stratified Miettinen-Nurminen (MN) method adjusted for age group.

A supportive analysis for the primary immunogenicity endpoints may also be performed using Per-Protocol Immunogenicity Set. For immune response against the BA.4/5 strain, in the ANCOVA model, antibody titers at Day 29 post-booster against the BA.4/5 strain will be a dependent variable, and a group variable (mRNA-1273.222 and mRNA-1273) will be the fixed effect, adjusting for age, pre-booster SARS-CoV-2 status, pre-booster titer if applicable; the model may also be adjusted for other characteristics. Age group (≥ 65 , < 65 years) or age as continuous variable may be considered in the ANCOVA model. The difference of SRR between mRNA-1273.222 and mRNA-1273 will be calculated with 95% CI based on stratified Miettinen-Nurminen method adjusted for pre-booster SARS-CoV-2 status and age group.

The primary immunogenicity objective (against BA.4/5 and ancestral SARS-CoV-2 D614G) is considered met if non-inferiority is demonstrated based on GMR and SRR difference, specifically:

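### The primary GMR models for the non-randomised comparisons in Parts F and G adjust age only as under 65 or 65 and over, and Part H leaves the coding open; age in years should be added alongside the age-group factor.

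*Protocol*

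**What the plan says.** Protocol Section 8.5.3.1.3 and the Synopsis give the Part F Cohort 1 model for Day 29 titre, in which the vaccine group "will be the fixed effect, adjusting for age groups". The full adjustment is "adjusting for age groups (< 65, ≥ 65 years) and prebooster antibody titer level, if applicable". SAP 6.4.3 has the same model and adds that "the model may also be adjusted for other characteristics", without naming any.

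The model is carried to the other Parts by reference. For Cohort 2 the Synopsis says "The same analyses methods described in Part F Cohort 1 will be used for Cohort 2". For Part G the SAP says "The analyses method described in Part F Cohort 1 will be used for Part G".

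Part H is treated differently in the two documents. The protocol (Synopsis and Section 8.5.3.1.5) says "The analyses methods described in Part F Cohort 1 will be used for Part H", which means the two-level factor. SAP 6.4.3 writes out a separate Part H model that adjusts for age, and says that age group "or age as continuous variable may be considered in the ANCOVA model". No rule selects between them. SAP Section 1 states: "If the methods in this SAP differ from the methods described in the protocol, the SAP will prevail".

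Only Part J is randomised (SAP 4.4). Age in years is summarised as a continuous variable (SAP 6.2.2).

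**The concern.** The comparisons that decide Parts F, G and H are between groups formed at different times or in different studies. Part F Cohort 1 is set against about 150 participants from study P201 Part B (SAP 4.6). The Cohort 2 control arm opens only after the mRNA-1273.529 arm is full, and Part G opens after that control arm. Part H was enrolled in August 2022 and its control in February 2022 (SAP 6.4.3). Nothing in this design balances age within a band, and with enrolment from age 18 the lower band runs from 18 to 64.

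A two-level factor removes only the difference in the proportion aged 65 and over. If one arm is younger within the lower band, and titre depends on age beyond what pre-booster titre captures, that difference is credited to the vaccine.

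The open coding in Part H is a separate weakness that does not depend on the size of any bias. The same mRNA-1273 control arm could be age-adjusted one way in Parts F and G and another way in Part H, with the choice made in an open-label study.

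**Working it through.** **1. Reproduce the plan's figures.** Inputs (protocol 8.3, SAP 4.3): SD of log titre 1.5, GMR margin 1.5, true variant GMR 1.5, true ancestral GMR 1. Reading the SD on the natural-log scale and multiplying component powers as if independent:

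- Part F, 300 vs 300, alpha 0.05: superiority 0.912 × SRR 0.983 = 0.896 (stated 89%).
- Part G, 300 vs 300, alpha 0.025: superiority 0.858 × ancestral non-inferiority 0.858 × SRR 0.967 = 0.711 (stated 71%).
- Part H, 300 vs 260, alpha 0.05: superiority 0.891 × ancestral non-inferiority 0.891 × SRR (5% margin) 0.773 × SRR (10% margin) 1.000 = 0.613 (stated 60%).

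Variant GMR non-inferiority is essentially 1 in each. The figures reproduce only when superiority is counted. No age term enters any of them.

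**2. How large a shift could be.** With no other covariate, the log-GMR moves by b = −ln(1 − decline per decade) × (gap in years)/10. Both inputs are assumptions:

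- 5% per decade, 2 years: factor 1.010.
- 10% per decade, 5 years: b = 0.1054 × 0.5 = 0.053, factor 1.054.
- 20% per decade, 10 years: factor 1.25.

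Pre-booster titre absorbs part of this. In a simulation with true GMR 1, 300 per arm, 25% aged 65 or over, and half the age effect carried by pre-booster titre, the age-group model gave 1.007 to 1.103 over the same ranges, and 1.024 in the middle case. A 5% shift is therefore possible but above the middle of the range.

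**3. What a shift b would do.**

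- SE, Part G = 1.5 × √(2/300) = 0.1225; z = 2.241.
- SE, Part H = 1.5 × √(1/300 + 1/260) = 0.1271; z = 1.960.
- Ancestral non-inferiority power = Φ((ln 1.5 − b)/SE − z), shift against the new vaccine.
- One-sided superiority error at true GMR 1 = Φ(b/SE − z), shift in its favour.

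| Assumed b | Part G power | Part H power | Part G superiority error | Part H superiority error |
|---|---|---|---|---|
| 0 | 86% | 89% | 1.25% | 2.5% |
| 0.02 | 82% | 86% | – | – |
| 0.05 | 75% | 80% | 3.3% | 5.9% |

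Example, Part G at b = 0.05: (0.4055 − 0.05)/0.1225 = 2.902; 2.902 − 2.241 = 0.661; Φ = 0.746.

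Part F has no primary ancestral test. Its superiority error at b = 0.05 would be 6.0% in Cohort 2 (SE 0.1225), and 5.2% in Cohort 1 with about 150 comparators (SE = 1.5 × √(1/300 + 1/150) = 0.15).

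**4. Which age coding to use.** When the assumed age effect is linear, linear age plus pre-booster titre returns 0.996 to 1.003, but that follows from the assumption. With a step at 65 instead, linear age in place of the group factor gave a GMR of 1.029 when the truth was 1. Keeping the group factor and adding age in years stayed within about 0.6% of the truth in all four age-effect shapes tried, with a standard error at most 3% larger.

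**The case against.** The strongest reply is that the harm is hypothetical. The documents report no age gap within a band and no age-titre slope. A reader might infer that the GMRs are confounded by age; the documents do not support that, nor a direction. This stands, and the figures above are illustrations only.

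A reader might also infer that the age term is the only safeguard. It is not. Pre-booster titre is in the model where applicable, other covariates may be added, the study arms share core eligibility criteria, the primary set is restricted to baseline-negative participants, and for Part H the SAP will examine baseline characteristics before comparing. These reduce the concern without closing it: the extra covariates are optional and unnamed, and no action follows from the Part H check.

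Nor is variant non-inferiority at risk at the planned GMR of 1.5: its power stays above 99.9% after a 5% shift in Parts F, G and H.

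Finally, the two-level factor is pre-specified consistently for Part F and matches the SRR stratification and subgroups. The SAP already describes immunogenicity assessments in the past tense (6.4.1), so replacing a primary covariate now could itself be a post-data choice. This stands and shapes the fix.

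**Conclusion.** A minor but real point. The Part F and G models leave within-band age differences unadjusted in comparisons that are not randomised, although age in years is available. The Part H coding is unsettled, and the protocol and SAP differ on it. Whether any GMR would move, by how much and in which direction cannot be told from the documents.

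Under an assumed 5% shift the exposed quantities are ancestral GMR non-inferiority in Parts G and H, with about 11 and 9 points of power lost, and superiority error in Parts F, G and H. With stated global powers of only 71% and 60% in Parts G and H, there is little slack. These results rest on the plan's SD of 1.5, its planned sample sizes, a normal approximation and the assumed shift. The superiority errors are for that single test and ignore the preceding non-inferiority gate.

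**What to change.** In SAP 6.4.3 and protocol 8.5.3.1.3, keep the two-level age factor and add age in years as a continuous covariate in the GMR ANCOVAs for Parts F, G and H. Delete the either/or sentence in the SAP's primary and supportive Part H models, so that one coding applies throughout and agrees with the protocol's cross-reference. Do not substitute linear age for the group factor.

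Where Day 29 results have already been analysed, state which coding was used, leave that primary model in place, and report the model with both age terms as a named sensitivity analysis.

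Keep the age-group split for the stratified SRR interval and the subgroup tables. Confirm that age in years is held for the P201 comparator; the existing split at 65 implies age data, but the documents do not say so.

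The cost is one degree of freedom, a standard error larger by 3% or less in the simulations, and a short edit. No new P205 data are needed.
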